### 21.1.3 Missing Data

Data collection will be monitored on an ongoing basis to ensure that the scores and imaging biomarkers are within the expected ranges and scales and missing data is rare. Multiple imputation will be used for missing data. Although we do not anticipate extensive missing data for a large proportion of participants in the study, participants with such extensive missing data (e.g.  $\geq 50\%$  cognitive scores) will be removed from analyses.

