### **8.3 Incomplete Visit Procedures and Protocol Deviations**

All attempts should be made to complete visit procedures as outlined in Appendix 1 within the allowable visit window period. On occasion, a participant might not be able to complete some of the required procedures (i.e., too impaired to complete the full cognitive assessment battery, unable to tolerate the full 60 minute MRI scan protocol, etc.) If a participant is unable to complete the full visit procedure as outlined in Appendix 1, the study team will document the reason for non-completion in the source documents. Participants will be followed as long as they are willing, and every attempt should be made to retain participants for longitudinal follow-up as long as possible. If participants are not willing or able to complete the full schedule of assessments at any visit, those assessments or procedures they are willing to complete should be conducted. It should be emphasized that the major priority

is to keep participants in the study, even if data collection is limited. If participants are no longer willing or able to travel to the clinic for annual visits, as much information should be collected via telephone as long as is possible, see section 8.7. Unless a participant has clearly declined brain autopsy, the neuropathology program should be discussed at each visit. Whenever a study procedure cannot be completed, sites will properly document the reason and review with the study team or IU IRB to determine if a protocol deviation is required.

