## **8.7 Remote Procedures**

Approved visit procedures depicted within the Schedule of Events (Appendix 1) can occur remotely any time it is not possible to conduct the visit in-person due to participant barriers. Remote activities can be conducted via telephone or video bridge. Neuropsychological batteries must be completed via video bridge following the virtual testing procedures manual. Examples of obstacles preventing participants from coming in-person to their visits may include disease progression, or inability to travel for any reason. When possible, participants should still come in-person to complete blood draw, LP, MRI and PET scans as applicable. A combination of remote and in-person data collection is allowed for the same visit. The study team will reassess participant ability to attend in person visits annually. If participants can resume in person visits, they will do so. If not, they will continue remote visit procedures. Prior approval from the IU team is required to conduct fully remote visits and confirmation of method of remote data collection, i.e. via telephone or video must be approved by IU and local regulatory body.

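### Section 21.1.3 removes whole participants with extensive missing data, which may select on severity and slightly understate EOAD decline

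*Protocol*

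**What the plan says.** Section 21.1.3 (Missing Data) gives a general method: "Multiple imputation will be used for missing data". It then sets an exception. Participants with extensive missing data, with 50% or more given as an example, "cognitive scores) will be removed from analyses". The unit removed is the participant, and the word analyses carries no limit to cognitive ones. The same sentence plays down the extent: "Although we do not anticipate extensive missing data for a large proportion of participants in the study".

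Section 8.3 (Incomplete Visit Procedures) is also measured about frequency: "On occasion, a participant might not be able to complete some of the required procedures". Its first example of why is being "too impaired to complete the full cognitive assessment battery". It says the major priority "is to keep participants in the study, even if data collection is limited", and falls back on the telephone when a participant can no longer travel.

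Section 8.7 (Remote Procedures) says that "obstacles preventing participants from coming in-person to their visits may include disease progression". It requires neuropsychological batteries to be done by video bridge. It also asks remote participants to attend for samples and scans: "When possible, participants should still come in-person to complete blood draw, LP, MRI and PET scans as applicable".

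Section 21.1.2 analyses longitudinal change under Aims 1 and 2 with mixed models, and under Aim 1 also with machine learning.

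**The concern.** The rule may select on severity. By the protocol's own account, people lose the cognitive battery or stop attending partly because they are too impaired or have progressed. A participant followed only by telephone cannot supply the battery at all, since section 8.7 requires video. Section 8.3 works to retain such people; section 21.1.3 may then discard what was collected from them.

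The trigger is cognitive scores, but the removal is from analyses in general. If the 50% is counted over scheduled visits, someone who lost only the battery could also lose observed CDR-SB, which Appendix 1 marks as possible remotely, and any MRI or PET attended in person. CDR-SB is one of the H1b outcomes.

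H1b and the longitudinal part of H2a compare rates of change between EOAD and ADNI LOAD. If the removed participants decline faster, the EOAD rate comes out too low. Aim 1 seeks outcome measures for future trials, so that rate matters beyond the H1b test.

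**Working it through.** The protocol gives no removal rate, slope SD or missingness mechanism, so there is no plan figure on this point to reproduce. Every input below is an assumption except the 650 EOAD participants (section 21.1.4) and the annual visits (Appendix 1).

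**1. Direction, analytically.** If a fraction f is removed from the worse tail of a normal variable that correlates ρ with decline, the mean slope of those who remain shifts toward less decline by ρ·φ(q)/(1−f) slope SDs, where q is the standard normal quantile at 1−f. For f = 0.05, q = 1.645 and φ(q) = 0.103, so the shift is 0.103/0.95 = 0.109 times ρ. That is 0.02 at ρ = 0.2 and 0.07 at ρ = 0.6. For f = 0.02 the range is 0.01–0.03; for f = 0.10 it is 0.04–0.12. At ρ = 0 it is zero.

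**2. Cognitive score, by simulation.** There are 300,000 participants per group, with visits at 0, 1, 2 and 3 years. The true slope is −1.0 per year in EOAD and −0.7 in LOAD; intercept SD 1, slope SD 0.7, residual SD 0.5. Loss of the battery is permanent and logistic in the last observed score (missing at random). A participant is removed if two or more of the four batteries are missing. The model is GLS with known covariance. Loss is tuned so that 2%, 5% or 8% of EOAD are removed (13 to 52 of 650).

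| Intercept–slope correlation | EOAD slope after the rule: 2% / 5% / 8% removed |
|---|---|
| −0.4 | −0.996 / −0.993 / −0.992 |
| 0 | −0.991 / −0.978 / −0.967 |
| +0.4 | −0.983 / −0.962 / −0.943 |

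Keeping everyone gives −0.998 to −1.001. The smallest attenuation is 1 − 0.996/0.998 = 0.2%; the largest is 1 − 0.943 = 5.7%. With both cohorts filtered, the EOAD–LOAD contrast is 0.288–0.298, against 0.296–0.302 with all data, so about 1–4% smaller. With missingness completely at random and 6% removed, the slope is −0.998 with or without the rule.

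**3. CDR-SB observed at all four visits, battery lost.** Baseline mean 3.5 (SD 1.8); slope 1.7 per year in EOAD and 1.0 in LOAD; slope SD 1.2, residual SD 0.8. Loss of the battery is logistic in current CDR-SB.

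| Correlation | Attenuation, permanent loss: 2% / 5% / 8% removed | Attenuation, intermittent loss: 2% / 5% / 8% removed |
|---|---|---|
| −0.4 | 1.2 / 2.7 / 4.2% | 2.0 / 4.4 / 6.5% |
| 0 | 1.7 / 3.8 / 5.8% | 2.3 / 5.2 / 7.7% |
| +0.4 | 2.1 / 4.8 / 7.2% | 2.6 / 5.8 / 8.7% |

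With both cohorts filtered, the contrast shrinks by 1.4–6.8% (permanent) or 3.1–9.2% (intermittent).

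**4. Missingness that depends on the unobserved current score.** With the set-up of step 2, the rule gives −0.968 to −0.894 and keeping everyone gives −0.979 to −0.938. At correlation −0.4 and 2% removed, the bias falls from 0.032 to 0.025, a reduction of 0.007/0.032 = 22%. At +0.4 and 8% removed, it falls from 0.106 to 0.051, a reduction of 0.055/0.106 = 52%.

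**5. Sensitivity to the inputs.** A separate simulation used 650 participants, mean slope −0.40, slope SD 0.30, intercept SD 1, residual SD 0.4, no intercept–slope correlation, and loss at random given the last score. Attenuation was 0.1% with 1.2% removed, 0.5% with 4.5%, 1.3% with 14% and 1.8% with 23%. Keeping everyone left a bias of 0.2% or less. Slopes vary less relative to intercepts here, so selection acts more on baseline level than on decline.

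**The case against.** The strongest objection is that the text does not say what the 50% counts. It is only an example, and it may mean half the tests in a battery rather than half the visits. On that reading the rule screens out profiles too sparse to form a composite score, which is a reasonable use. Follow-up is also open-ended, so a denominator of four visits is not the protocol's own. This stands as a limit on the figures, and the loss of CDR-SB and imaging data depends on the visit reading.

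A remote visit is not missing data. Section 8.7 allows the battery by video, and Appendix 1 marks the main cognitive measures and CDR as possible remotely. Failing to finish the full battery is also not the same as missing half of it. This narrows the route to removal mainly to telephone-only contact and badly incomplete batteries; it does not close it.

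The magnitudes are assumed and unstable. At about 5% removed, step 5 gives 0.5%, against 0.7–3.8% for the cognitive score in step 2 and 2.7–5.8% for CDR-SB in step 3. Step 3 also supposes that CDR-SB is always obtained while the battery is lost, which is unfavourable to the rule. The percentages therefore illustrate the mechanism and are not properties of this study.

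The consequence for inference is limited. If LOAD is filtered alike, which the section does not say, the effect partly cancels, and what remains works against H1b, so the test errs on the conservative side.

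Finally, details of analysis sets often belong in an SAP, which is not at hand. But the protocol does not leave this open: it states the removal.

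**Conclusion.** The concern holds as a possible, slight bias that can be avoided. Removal is stated for whole participants, the protocol links some of the missing data to impairment and progression, and the planned mixed models and imputation do not need it. If those removed decline faster, EOAD decline is understated; if missingness is unrelated to severity, almost nothing is lost.

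The size is unknown and probably small: under the assumed inputs, at most a few percent of the EOAD slope for a cognitive score and under 9% for CDR-SB. These figures rest on the visit reading of the 50%, on 2–8% of EOAD being removed, and on the assumed variances and loss models. A change is worth making because it is cheap and keeps data from participants the study works to retain, not because a large error has been shown.

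**What to change.** In section 21.1.3, state that the regression and mixed-model analyses include every participant with at least one usable observation of the outcome, by a likelihood-based mixed model or the multiple imputation already planned. Limit the 50% removal rule to clustering and machine-learning steps that need complete score profiles, and otherwise use it only as a sensitivity analysis.

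This takes one or two sentences and no extra data. The price is that the main analysis relies on missing at random. If missingness depends on the unobserved current score, the change reduces the bias (by about 22–52% in step 4) but does not remove it.

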### 21.1.4 Sample Size

Sample size considerations were developed for each aim and are presented below. The computations of sample size assumed a target power of 90% at significance level of 0.05. A total sample size of 650 EOAD participants is envisioned for the study. The specific effect sizes for each of the aims are presented below. In general, these effect sizes are smaller or equal to those observed in our preliminary data.

#### **Aim 1**

We will have 90% power to identify a -0.26 group difference in mean composite cognitive Z-scores between EOAD and LOAD participants after controlling for episodic memory performance. We will have 90% power to detect an average difference of 0.7 in decline in CDR-SB between EOAD and ADNI LOAD.

Similarly, we will have 90% power to identify an effect size of -1.5 for decline in MMSE.

#### **Aim 2**

We will have 90% power to detect cross-sectional differences in cortical gray matter volumes of at least -0.2. We will have 90% power to detect a cross-sectional difference of  $0.2 \text{ mm}^3$  in flortaucipir SUVR. For longitudinal data, we will have 90% power to detect a difference of -0.001 in annualized Jacobian values between EOAD and LOAD in the region-of-interest. Preliminary longitudinal flortaucipir data in EOAD were too sparse to estimate effect size or power. We will have power of 90% to observe correlations of 0.1 or greater between MRI/ flortaucipir and clinical composite scores - these correlations are considerably lower than the smallest flortaucipir-cognitive correlations observed in our preliminary data.

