#### **Aim 2**

MRI and PET based biomarker volumes computed at the mm^3 scale, will be used to assess baseline and longitudinal associations of composite cognitive scores and imaging metrics and identify differences between LEADS EOAD and ADNI LOAD participants. Specifically, multiple linear regression analysis will be used to identify differences between imaging-based metrics in LEADS EOAD vs. ADNI LOAD at baseline and to assess correlations between composite cognitive and imaging measures, while longitudinal data will be analyzed using mixed effects models when data for more than 2 visits per participant is collected. Relevant confounders (e.g. sex, education) will be included as covariates. In addition, summary MRI and PET measures will be analyzed using machine learning techniques to identify a composite metric capturing change across LEADS EOAD participants.

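### Aim 2 claims 90% power for correlations of 0.1 or greater, but 650 EOAD participants at alpha 0.05 give about 72%; 90% is reached at about 0.127

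*Protocol*

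**What the plan says.** Section 21.1.4 sets common inputs before it goes through the aims: "The computations of sample size assumed a target power of 90% at significance level of 0.05", and "A total sample size of 650 EOAD participants is envisioned for the study". No other sample size appears in that section, and it does not say whether tests are one-sided or two-sided.

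The Aim 2 paragraph of that section then states: "We will have power of 90% to observe correlations of 0.1 or greater between MRI/ flortaucipir and clinical composite scores". It adds that "these correlations are considerably lower than the smallest flortaucipir-cognitive correlations observed in our preliminary data".

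The matching analysis is in Section 21.1.2, Aim 2. Multiple linear regression is to be used to compare imaging metrics between LEADS EOAD and ADNI LOAD at baseline "and to assess correlations between composite cognitive and imaging measures". On adjustment it says: "Relevant confounders (e.g. sex, education) will be included as covariates". Mixed models are planned for longitudinal data. The hypothesis served is H2b in Section 3.2, which relates tau, atrophy and fluid measures to cognition and names no cohort.

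**The concern.** The power of a test of zero correlation depends only on the correlation, the sample size and alpha. It needs no standard deviation or unpublished pilot value, so this is one of the few power statements in the section that a reader can check from the protocol alone. A correlation of 0.10 is small, and 650 participants looked too few to detect it with 90% power.

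Readers of H2b, and later users of this shared cohort, would take 0.10 as the smallest correlation the study can reliably detect. If power there is well below 90%, a non-significant imaging-cognition association would be read as stronger evidence of absence than it is.

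**Working it through.** **Inputs**

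- Sample size n = 650 EOAD, alpha = 0.05 and target power 90% (Section 21.1.4, opening paragraph).
- Correlation r = 0.10 (Section 21.1.4, Aim 2).
- Sidedness is not stated, so both are tried.

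**Formula.** By Fisher's z, power = Φ( atanh(r) × √(n − 3) − z_α ), with z_α = 1.960 two-sided or 1.645 one-sided.

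**1. Attempt to reproduce the stated 90%**

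atanh(0.10) × √647 = 2.552.

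- Two-sided: 2.552 − 1.960 = 0.592; Φ(0.592) = 72.3%.
- One-sided: 2.552 − 1.645 = 0.907; Φ(0.907) = 81.8%.

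Neither gives 90%. The noncentral t distribution gives 72.5% and 82.0%. A simulation of 40,000 data sets gives 72.2% and 81.7%.

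**2. Effect of covariates.** Adjusting for two covariates (sex and education) replaces √647 with √645. Two-sided power is then 72.2%, so adjustment does not explain the gap.

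**3. Correlation detectable with 90% power at n = 650**

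- Two-sided: tanh( (1.960 + 1.2816) / √647 ) = 0.127.
- One-sided: tanh( (1.645 + 1.2816) / √647 ) = 0.115.

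**4. Sample size needed for 90% power at r = 0.10**

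- Two-sided: ( 3.2415 / atanh(0.10) )² + 3, which rounds up to 1,047, or 397 more than 650.
- One-sided: ( 2.9264 / atanh(0.10) )² + 3, which rounds up to 854.

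**5. Two-sided power near the stated threshold, n = 650**

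| True correlation | Power |
|---|---|
| 0.10 | 72.3% |
| 0.11 | 80.2% |
| 0.12 | 86.6% |
| 0.13 | 91.4% |

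**6. Other sample sizes at r = 0.10**

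| Basis | n | Sides | Power |
|---|---|---|---|
| US cognitively impaired (650 + 200) | 850 | two | 83.2% |
| US cognitively impaired | 850 | one | 89.9% |
| All cognitively impaired (850 + 40) | 890 | one | 91.0% |
| All LEADS participants (890 + 110 CN) | 1,000 | two | 88.7% |
| EOAD plus an equal number of ADNI LOAD (assumed 1:1) | 1,300 | two | about 95% |

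For the last row: atanh(0.10) × √1297 − 1.960 = 1.65; Φ(1.65) is about 95%.

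**7. Missing data.** The section makes no allowance for it. If 10% of the 650 had no usable pair of measurements (an illustrative assumption), n = 585, two-sided power at 0.10 is 67.7%, and the correlation detectable with 90% power is 0.134.

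**The case against.** The best defence is that 650 is the EOAD total for the study, and nothing ties it expressly to this correlation. In Section 21.1.2 the correlation shares a sentence and a regression model with the EOAD versus LOAD comparison. Section 1.0 says ADNI has up to 2,000 LOAD participants, far more than the 397 extra needed, and H2a speaks of matched LOAD participants. In a pooled analysis of sufficient size, the stated power would be correct or conservative. This shows that the intended basis may differ from 650. It does not supply that basis: the protocol gives no LOAD number or matching ratio and does not say the correlation is pooled. The 850 and 890 figures would also need an unstated one-sided test and the EOnonAD cohort, whose analysis Section 21.1.2 calls exploratory.

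Rounding is a second explanation. The effect sizes in the Aim 2 paragraph carry one significant figure, and 0.127 becomes 0.1 in that form. This is plausible. But the sentence says "correlations of 0.1 or greater", which makes the rounded value a lower limit, and rounding a detectable effect down overstates power.

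The third argument is that it hardly matters. Much of this stands. No treatment decision depends on the test, and preliminary flortaucipir-cognition correlations are said to be considerably larger. That comparison does not mention MRI, but Section 21.1.4 also says that effect sizes across the aims are in general no larger than those in the preliminary data, which eases the concern for MRI. None of this makes the stated power correct.

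**Conclusion.** The stated power does not follow from the section's own inputs. With 650 EOAD participants and alpha 0.05, a correlation of 0.10 has about 72% power two-sided, or 82% one-sided, against the 90% claimed. The type II error at the stated threshold is 28% instead of 10%, and the correlation detectable with 90% power is about 0.127.

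This rests on the analysis using the 650 EOAD participants, on complete data, and on a test at a single time point. The planned longitudinal mixed models were not assessed. If a pooled population was intended, the sentence could be correct, but the protocol would still need to say so. The consequence is modest: H2b has more than 90% power for correlations of 0.13 and above.

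**What to change.** Restate the sentence in Section 21.1.4, Aim 2: with 650 EOAD participants and two-sided alpha 0.05, there is 90% power to detect correlations of about 0.13 or greater, and about 72% power at 0.10. If a pooled sample (for example with ADNI LOAD) or a one-sided test was intended, keep 0.10 and state the population, its size and the sidedness.

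The cost is one sentence. Enrolment, visits and the planned analysis do not change.

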#### **Aim 3**

Assuming  $\sim 50\%$  *APOE4+*, we will have 90% power to detect a difference of 20% in the proportion of non-amnestic (lvPPA/PCA) participants in *APOE4+* vs. *APOE4-* participants. We will have 90% power to detect a cross-sectional mean difference in TIV-adjusted MTL volume of -4.4 ml between carriers and non-carriers and an average difference in flortaucipir MTL SUVR 0.1 between the two groups.

#### **Aim 4:**

When testing 171 genes in AD pathways, we have 80% power to detect genes contributing to disease risk having an odds ratio of 1.5-3.0 if we assume 50% of the variants retained following filtering contribute to disease risk/resilience (alpha =  $2.9 \times 10^{-4}$ ).

**APPENDIX 1** **SCHEDULE OF EVENTS**  
**All (EOAD, EOnonAD, and CN) Participants– Screening and Baseline**

Procedure	Visit	Screening a	Baseline a	Genetics Status Disclosure
Window Period (days)	≤ 60			See footnote b
Informed Consent u	X			
Brain donation discussion/provisional consent c,u			X	
Vital Signs	X			
Neurological and Physical Exams	X			
Demographics & Medical History u	X			
Clinical Diagnosis and Clinical Symptom Assessment	X			
Family History u	X			
Early Developmental History Questionnaire u			X	
Autoimmune History Questionnaire u			X	
Sex and Reproductive Health Questionnaire u			X	
Area Deprivation Index u,w			X	
Concomitant Medications u	X			
NACC UDS and FTLD Modules, and Neuropsychological Battery d,u	X e,f			
MMSE u	X e			
Digit Symbol	X f			
Amsterdam IADL Questionnaire u	X f			
ADAS-Cog13 u	X f			
Rey Auditory Verbal Learning Test (RAVLT) u	X f			
TabCat: Flanker, Line Length, Line Orientation, and Match			X	
CDR u	X			
Pregnancy Test g	X	X		
3T MRI/fMRI i	X h			
Amyloid PET Scan			X j	
Tau PET Scan v			X j	
Adverse Event u			X	
Genetic Counseling o,t,u			X k	
Amyloid & Tau Status Disclosure u,v			X l	
PET Scan: FDG r			X m	
FDG Status Disclosure u			X ml	
Wellness Check n,u			X	
Study Participation Report o			X	
Blood for Genetic testing p			X	
Blood for AD blood biomarkers r , DNA, and RNA, PBMC q			X	

LP Safety Labs (CBC, coagulation profile)	X		
Lumbar Puncture (optional) r,s		X	

a) Visit procedures may be split over multiple days without constituting a protocol deviation.
 
b) Timing for result disclosure is not set and dependent on the availability of the genetic screening results.
 
c) Post mortem brain donation discussion to confirm consent/interest. If participant refuses to participate, no further inquiry should take place. Undecided participants will be approached at each study visit until they consent or refuse to participate.
 
d) The NACC UDS and FTLD modules include demographics, clinical, cognitive, functional, and behavioral assessments.
 
 
• Version C2 the NACC UDS Neuropsychological Battery will be used in this study
 
• UDS forms A1, A3, A5, B4-B9, C2, D1, and D2 are required for LEADS
 
• UDS forms A5/D2, D1a, and D1b will take the place of A5, D2, and D1 if using UDSv4
 
• FTLD forms B3F, B9F, C1F-C6F, E2F, and E3F are required for LEADS
 
 
e) The MMSE and MoCA cannot be administered on the same day. MMSE is required at screening to confirm CN eligibility. MMSE can be done anytime between screening and baseline for CI participants.
 
f) Can be conducted anytime between screening and baseline for CI participants if sufficient testing has been completed to meet NIA-AA criteria for MCI due to AD or probable AD. These activities must occur at Screening for CN participants.
 
g) If a female is not surgically sterile or post-menopausal by two years, a pregnancy test will be performed prior to amyloid, tau, and FDG PET. Only participants with a negative result will be eligible for PET scanning.
 
h) The first MRI scan should be done at screening unless a previously existing MRI within 12 months can be used to assess overall eligibility and safety prior to LP procedure. If a previous scan is not available, the study MRI must be completed at the Screening Visit to facilitate eligibility determination. A study MRI must be completed within the 60 day visit window regardless of a pre-existing MRI being used to assess study eligibility. See section 7.6.4 for more detail.
 
i) All attempts should be made to acquire the full 60 minute MRI protocol; however the MPRAGE and 3D FLAIR should be prioritized. The MPRAGE and 3D FLAIR are the mandatory sequences for enrollment. If needed, the other sequences may be skipped for any reason without constituting a protocol deviation. Note the reason for non-completion in the source documents.
 
j) The amyloid and tau PET scans can be conducted anytime between screening and baseline following MRI. Inclusion/exclusion must be confirmed prior to both scans. The amyloid and tau PET scans must be conducted at least 12 hours apart.
 
k) At the Screening Visit, EOAD and EOnonAD participants will view a video that will discuss the implications of mutations in known ADAD loci. The participant will also be asked if they would like to speak with a genetic counselor to verify their understanding of the implications of genetic testing and answer any questions the participant may have. These participants at international sites may meet with a genetic counselor or investigator with appropriate clinical training in genetic counseling as opposed to watching the video. Written informed consent will be obtained on all participants prior to genetic testing (see section 7.2 Genetic Counseling and Testing section for more detail). Disclosure will be performed as outlined in section 7.1.6.
 
l) Amyloid and tau disclosure is required for EOAD and EOnonAD participants only and should be conducted between screening and baseline. Amyloid disclosure should be conducted within the 60 day visit window. Tau disclosure may be conducted outside of the 60 day visit window due to the timing of the scan and availability of the PET read. FDG PET disclosure is required for EOnonAD participants only. FDG disclosure may be conducted outside of the 60 day visit window due to the timing of the scan and availability of the PET read.
 
m) The FDG PET scan at Baseline applies to CN and EOnonAD participants only. EOAD participants do not receive an FDG PET scan. The FDG PET scan for EOnonAD participants cannot be scheduled until after amyloid disclosure. For sites that have radiation safety committees (RSC), ability to conduct FDG PET scans will also be contingent on local RSC approval.
 
n) To be completed within 48 hours of lumbar puncture. Additionally, a telephone call will be made within two weeks post amyloid results disclosure. See section 7.1.4 for more detail.
 
o) May be provided to participants at the discretion of the PI. See section 7.1.8 for more detail.
 
p) Blood for genetic testing will be drawn for EOAD and EOnonAD participants only; CN participants will not have blood drawn for genetic testing.
 
q) PBMC samples must be collected and shipped the same day. Fasting is not required. PBMC sample collection is optional for international sites. If collected, international sites will store PBMC samples locally. See NCRAD Biospecimen, Collection, and Shipping manual for more details.
 
r) LP should be collected after a minimum 6-hour fast (preferably in the morning after an overnight fast). FDG-PET should be collected after an overnight fast for scans conducted in the morning, or a minimum 4-hour fast for scans collected later in the day; prior to the scan, a blood glucose measurement will be made by finger stick and scans will be postponed or rescheduled if the reading is > 180 mg/dL.
 
s) Can be conducted anytime between screening and baseline. Completion of safety lab report and MRI review with PI signature are required prior to LP. See section 7.6.2 for more detail.
			

- t) The CN cohort does not receive their genetic results and therefore do not require genetic counseling. Positive genetic results require genetic counseling for the CI cohort if they have agreed to receive their genetic results. Participants at international sites may speak with the site PI or appropriately trained clinical investigator.
- u) Visit procedures noted with "u" can be completed remotely. See section 8.7 for more information. See the procedures manual for more information on collecting the NACC UDS and FTLD modules remotely.
- v) Tau PET scan is not required for select international sites. Participants from select international sites will not complete tau PET scans and therefore will not receive tau PET results.
- w) The Area Deprivation Index is only collected at U.S. sites.

(continued on next page)

